5.1 Missing data

The number of missing observations and the associated reasons will be reported. For the primary outcome, fall rates, missing data will not be imputed; however, the analysis will be adjusted for follow-up time (days of follow-up will be used as an offset). Likewise, missing data regarding the secondary binary outcomes will neither be imputed, but the modified Poisson regression will be adjusted for person-years (days of follow-up will be used as an offset). For participants who do not return any fall calendars 0 falls and 0 person-years will be registered. However, if more than 10% of data is missing in any outcomes, a sensitivity analysis utilising multiple imputations will be conducted.

Missing data in continuous outcome are expected to be missing at random; thus, they will not be imputed as it has shown that multiple imputations do not add any benefits to a linear mixed-effects model.[25]

6. Statistical Analysis

All statistical tests will be performed using an intention-to-treat approach. Moreover, a per-protocol analysis will also be performed, including only participants who complete 75% or more of the training sessions. The secondary outcome will not be adjusted for multiple comparisons; thus, these results should be considered exploratory.

Count data will be reported as incidence rate ratios (IRR) with 95% confidence intervals (95% CI). Binary outcomes will be reported as risk ratios (RR) and 95% CIs. When appropriate, continuous variables will be reported as either mean and standard deviation or median and interquartile range.

Table 1 Variables, measures, and methods of analysis for fall outcomes.

Primary outcome					
Variable/outcome	Mode of assessing	Time frame	Variable type	Assumption	Methods of analysis
Fall rate (falls per person-year)	Fall calendars	Continuously for 12 months	Count	Equal mean and variance *	Poisson regression Alternative: Bootstrapping [†]
Secondary fall outcomes					
Variable/outcome	Mode of assessing	Time frame	Variable type	Assumption	Methods of analysis
Proportion of fallers	Fall calendars	Continuously for 12 months	Binary	Equal mean and variance *	Poisson regression with robust error variance
Time to first fall	Fall calendars	Continuously for 12 months	Survival	Linear relationship between log hazard and covariate ^a	Cox proportional hazard
Fall-related fracture rate	Fall calendars	Continuously for 12 months	Count	Equal mean and variance *	Poisson regression Alternative: Bootstrapping [†]
The proportion with a fall-related fracture	Fall calendars	Continuously for 12 months	Binary	Equal mean and variance *	Poisson regression with robust error variance
Fall-related injury rate (other injuries than fractures)	Fall calendars	Continuously for 12 months	Count	Equal mean and variance *	Poisson regression Alternative: Bootstrapping [†]

The proportion with fall-related injuries (other injuries than fractures)	Fall calendars	Continuously for 12 months	Binary	Equal mean and variance *	Poisson regression with robust error variance
Fall-related hospital contact rate	Fall calendars	Continuously for 12 months	Count	Equal mean and variance *	Poisson regression Alternative: Bootstrapping [†]
The proportion with a fall-related fracture	Fall calendars	Continuously for 12 months	Binary	Equal mean and variance *	Poisson regression with robust error variance
All-cause fracture rates	Fall calendars	Continuously for 12 months	Count	Equal mean and variance *	Poisson regression Alternative: Bootstrapping [†]
The proportion with an all-cause fracture	Fall calendars	Continuously for 12 months	Binary	Equal mean and variance *	Poisson regression with robust error variance
Patient Global Impression of Change	7-item questionnaire and 11-point Likert scale; proportion “4 – somewhat better”) and 0-11 points on the Likert scale (lower score indicates better performance)	52-week follow-up	7-item questionnaire: Binary VAS: Continuous (Ordinal)	VAS-scale: Normal distribution [‡] Homogeneity of variance [‡]	7-item questionnaire: Fisher’s Exact VAS-scale: Unpaired t-test Alternative: Unpaired two-sample Wilcoxon test [‡]
Laboratory-induced overall fall rate	Visual inspection of video recording of a level 1 slip and trip perturbation; fall (1) or no fall (0)	Pre-training test; post-training test; 26- week follow-up; 52-week follow-up	Count	Equal mean and variance *	Poisson regression Alternative: Bootstrapping [†]

Laboratory-induced slip falls	Visual inspection of video recording of a level 1 slip perturbation; fall (1) or no fall (0)	Pre-training test; post-training test; 26- week follow-up; 52-week follow-up	Binary	-	Fisher's Exact
Laboratory-induced trip falls	Visual inspection of video recording of a level 1 trip perturbation; fall (1) or no fall (0)	Pre-training test; post-training test; 26- week follow-up; 52-week follow-up	Binary	-	Fisher's Exact

* Similarity of the calculated mean and variance; † If mean is not equal to variance; ^a Visual inspection of residual plots; [‡] Examined by visual inspection of histograms and QQ-plots; [‡] If data is not normal-distributed; ^o Participants ID as randoms effect - only participants, who did not fall during the perturbation at pre-training test was included

Table 2 Variables, measures, and analysis methods for fall-related risk factors.

Variable/outcome	Mode of assessing	Time frame	Variable type	Assumption	Methods of analysis
Single- and dual-task gait speed	6-meter walking test; walking speed (m/s)	Pre-training test; post-training test; 26- week follow-up; 52-week follow-up	Continuous (ratio)	Normal distribution of residuals and random effects ^{*‡} Homogeneity of variance [‡]	Linear mixed-effects model ^o

Single- and dual-task sway	30-second balance test on WBB [†] ; centre of pressure area (mm ²) and velocity (mm/s)	Pre-training test; post-training test; 26- week follow-up; 52-week follow-up	Continuous (ratio)	Normal distribution of residuals and random effects * [◊] Homogeneity of variance [◊]	Linear mixed-effects model [○]
Choice stepping reaction time (CSRT)	CSRT on WBB [†] ; reaction time (ms)	Pre-training test; post-training test; 26- week follow-up; 52-week follow-up	Continuous (ratio)	Normal distribution of residuals and random effects * [◊] Homogeneity of variance [◊]	Linear mixed-effects model [○]
Short physical performance battery	2x4 meter walking time, 3x10 second static balance with 3 different foot positions, and 5 chair raises; score from 0-12 (higher score indicates better performance)	Pre-training test; post-training test; 26- week follow-up; 52-week follow-up	Continuous (ordinal)	Normal distribution of residuals and random effects * [◊] Homogeneity of variance [◊]	Linear mixed-effects model [○]
Trial-making-test Part A and B; time and error	Part A and Part B of the Trail-making-test; time (s) and errors (n). Difference in time-to-complete between Part A and Part B; time (s)	Pre-training test; post-training test; 26- week follow-up; 52-week follow-up	Continuous (ratio)	Normal distribution of residuals and random effects * [◊] Homogeneity of variance [◊]	Linear mixed-effects model [○]
Short Falls Efficacy Scale	7-item questionnaire; score from 7-28 (lower score indicates better performance)	Pre-training test; post-training test; 26- week follow-up; 52-week follow-up	Continuous (ordinal)	Normal distribution of residuals and random effects * [◊] Homogeneity of variance [◊]	Linear mixed-effects model [○]

EuroQoL 5D-5L	
5-item questionnaire and visual analogue scale; index from 0-1 (higher score indicates better performance)
 
Visual analogue scale from 0-100 (higher score indicates better performance)
	
Pre-training test; post-training test; 26-week follow-up; 52-week follow-up
	
Continuous (ordinal)
	
Normal distribution of residuals and random effects^{*†} Homogeneity of variance[‡]
	
Linear mixed-effects model[○]

---------------	---	--	-----------------------------	---	---

* Examined by visual inspection of histograms and QQ-plots; [†] Examined by visually inspecting residuals plotted against fitted values; [‡] If data is not normal-distributed; [‡] Violations of assumptions will be noted; however, no alternative method will be used, as the linear mixed-effects model is robust against such violations; [○] Participant ID as the random effect

Sensitivity analysis

Fall outcomes

For the primary outcome (fall rates) and secondary fall outcomes, a sensitivity analysis adjusting for known confounders (age, sex, and previous falls) will be conducted to evaluate the robustness of the results. Furthermore, if the count variable data is over-dispersed, a poisons regression with bootstrapping will be performed; however, a sensitivity analysis without bootstrapping will also be carried out. These analyses were planned before the commencement of data collection. Additional fall rate sensitivity analyses 1) only including participants with no prior history of falls 12 months before study commencement and 2) only including participants with a history of falls 12 months before study commencement will also be conducted. These sensitivity analyses were planned after data collection began.

Fall-related risk factor outcomes

Before data collection commenced, it was determined to conduct a sensitivity analysis on the secondary fall-related risk factors adjusting for age, sex, and previous falls will be carried out.

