6.3. Major Protocol Deviations

Major protocol deviations will be reported in the trial registration at ClinicalTrials.gov ([NCT04733222](https://clinicaltrials.gov/ct2/show/NCT04733222)), the local ethics committee, and the SAP.

7. Implementation of Analysis Plan

The data will be exported from REDCap to the statistical program STATA. An external statistician not involved in the study will assist with the statistical test.

STATA CODE

Poisson regression (example of code for fall rate):
poisson fallrate ib1.group, irr exposure(personyear)

Poisson regression with bootstrapping (example of code for fall rate):
poisson fallrate ib1.group, irr exposure(personyear) vce(bootstrap, reps(1000))

Poisson regression adjusting for age, sex, and fall history (example of code for fall rate):
poisson fallrate ib1.group age i.sex i.prev_faller, irr exposure(personyear)

Poisson regression with robust error variance (example of code for proportion of fallers):
glm faller ib1.group, fam(poisson) link(log) vce(robust) eform

Poisson regression with robust error variance adjusting for age, sex, and fall history (example of code for proportion of fallers):
glm faller ib1.group age i.sex i.prev_faller, fam(poisson) link(log) vce(robust) eform

Cox survival analysis (example of code for time to first fall):
stset firstfall, failure(faller==1)
stcox group

Cox survival analysis adjusted for age, sex, and fall history (example of code for time to first fall):

```
stset firstfall, failure(faller==1)  
stcox group age i.sex i.prev_faller
```

unpaired t-test (example of code for Global Patient Impression of Change (gpic)):

```
ttest gpic, by(group) unpaired
```

Unpaired two-sample Wilcoxon test (example of code for Global Patient Impression of Change):

```
ranksum gpic, by(group)
```

Fisher's exact (example of code for the proportion of fallers following slip perturbation at pre-training (t1)):

```
tabulate lab_slip_t1 group, exact
```

Linear mixed-effects model (example of code for single-task gait speed):

```
mixed gaitspeed_st group time || record_id:, var reml
```

In case of significant interaction effect, a posthoc analysis adjusted using the Bonferroni method is employed using the following code:

```
contrast rb1.time#group, mcompare(bonferroni)
```

Linear mixed-effects model adjusting for age, sex, and fall history (example of code for single-task gait speed):

```
mixed gaitspeed_st age i.sex i.prev_faller group##time || record_id:, var reml
```

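### The plan promises a follow-up offset for the binary fall outcomes, but the code for the proportion of fallers leaves it out, so participants with no calendars can be counted as non-fallers for the full year

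*Combined protocol and SAP*

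**What the plan says.** Section 5.1 sets three rules for the binary fall outcomes.

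- No imputation: "missing data regarding the secondary binary outcomes will neither be imputed".
- An offset: "the modified Poisson regression will be adjusted for person-years (days of follow-up will be used as an offset".
- A rule for complete non-return: "For participants who do not return any fall calendars 0 falls and 0 person-years will be registered".

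It adds a safeguard: "if more than 10% of data is missing in any outcomes, a sensitivity analysis utilising multiple imputations will be conducted". Section 6 fixes the effect measure: "Binary outcomes will be reported as risk ratios (RR) and 95% CIs".

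The Stata code in section 7 gives two commands for the proportion of fallers. The unadjusted one is "glm faller ib1.group, fam(poisson) link(log) vce(robust) eform" and the adjusted one is "glm faller ib1.group age i.sex i.prev_faller, fam(poisson) link(log) vce(robust) eform". Neither has `exposure()` or `offset()`. All three fall-rate commands do have the term; the unadjusted one begins "poisson fallrate ib1.group, irr exposure(personyear". Table 1 names Poisson regression with robust error variance for the calendar-based binary outcomes and does not mention an offset.

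**The concern.** The text and the code treat the same people differently.

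- **No calendars returned.** Under the text, zero person-time carries no information. Under the code every row has the same exposure, so a registered zero becomes a full year without a fall, provided `faller` is built from registered falls. The plan does not show how `faller` is built. In effect this imputes no fall, which section 5.1 rules out.
- **Partial follow-up.** People who leave early keep their recorded falls but are treated as fully observed. This happens however the no-calendar group is coded.
- **The safeguard.** The plan does not say whether a registered 0 counts as missing, so these participants may not count toward the 10% trigger for multiple imputation.

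The proportion of fallers is the one secondary fall outcome with a stated hypothesis (section 2.2: 50% lower with PBT). Having two versions also leaves a choice of model open after the results are known.

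**Working it through.** **The plan's own figure.** Section 3.1 gives 70 per group for the fall rate (rate 0.85, rate ratio 0.5, 80% power, 5% level taken as two-sided, 20% dropout). A Poisson Wald calculation with the null variance at the overall mean rate gives

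N = (1.96·√5.333 + 0.842·√6)² / (0.85·(ln 0.5)²) = 106.3,

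or 54 per group, and 54/0.8 gives 68 after rounding up. This is close to 70 when 0.85 is read as the control rate, the reading used below. The point here does not depend on the sample size.

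**Expected 12-month risks.** With P(faller) = 1 − exp(−rate):

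- Control: 1 − exp(−0.85) = 0.573
- PBT: 1 − exp(−0.425) = 0.346
- Ratio: 0.605

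**Participants with no calendars.** If a share w of an arm is coded as non-faller, its observed proportion is multiplied by (1 − w). The bias factor on the risk ratio is (1 − w_PBT)/(1 − w_control). The documents do not give w, so these shares are assumptions.

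| No calendars, PBT vs control | Factor | 0.605 becomes |
|---|---|---|
| 5% vs 2.5% | 0.95/0.975 = 0.974 | 0.59 |
| 2.5% vs 5% | 0.975/0.95 = 1.026 | 0.62 |
| 20% vs 10% (14 and 7 of 70) | 0.80/0.90 = 0.889 | 0.54 |
| 10% vs 20% | 0.90/0.80 = 1.125 | 0.68 |
| Equal | 1.00 | 0.605 |

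With 10% non-return in both arms the ratio holds, but the control proportion is reported as 0.573 × 0.90 = 0.515.

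**Effect on an interval.** These use whole-number expected fallers and 70 per arm.

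- No calendars for 7 PBT and 14 control, fallers 22 and 32. As coded: (22/70)/(32/70) = 0.688 (95% CI 0.447 to 1.057). Zero-person-year rows left out: (22/63)/(32/56) = 0.611 (0.407 to 0.917).
- No calendars for 14 PBT and 7 control, fallers 19 and 36. As coded: 0.528 (0.338 to 0.825). Left out: 0.594 (0.389 to 0.907).

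**Partial dropout.** Suppose a share d leaves uniformly over the year, L = 0.85 in both arms, and there is no true effect.

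- Proportion observed to fall: (1 − d)(1 − e^−L) + d[1 − (1 − e^−L)/L]. This is 0.523 at d = 0.20 and 0.548 at d = 0.10.
- Mean person-years: 1 − d/2, so 0.90 and 0.95.
- 20% PBT vs 10% control: 0.955 without the offset; (0.523/0.90)/(0.548/0.95) = 1.008 with it.
- 10% vs 20%: 1.047 without and 0.992 with.
- 20% vs 20%: 1.00 either way.

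**Imputation trigger.** In the 14-and-7 case, 21/140 = 15% have no outcome data. That exceeds 10% only if these participants count as missing.

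**The case against.** The strongest reply is that the main harm depends on a step the plan does not document. If `faller` is left missing for people with no calendars, which fits the no-imputation rule, the no-calendar bias disappears even without the offset. That is a fair reading, and it is why the consequence is put conditionally. It does not help with partial dropouts, and no text says that `faller` is set to missing.

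The commands are also labelled as examples, so the omission may be a drafting slip set against an explicit rule. It may be, but they are the only commands given for these models.

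On size, the 20% in section 3.1 is overall dropout, not total non-return, so the 20% against 10% cases are upper-end illustrations. The mild case shifts log RR by 0.026, about one-seventh of the standard error of 0.19; the larger case shifts it by 0.12, about 0.6 of a standard error. The absolute proportions, partial-dropout ratios and standard errors assume no over-dispersion, though the no-calendar factors do not. All of this stands, as does the fact that secondary results are declared exploratory.

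Time to first fall is also analysed by Cox regression, which can allow for censoring. That is a separate outcome and does not repair the risk ratio.

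**Conclusion.** The contradiction is real: run as coded, the analysis of the proportion of fallers is not the one section 5.1 describes. If `faller` is derived from registered falls and non-return differs by arm, the risk ratio is biased in favour of the arm that loses more. The factor is about 0.97 or 1.03 for 5% against 2.5%, and up to 0.89 or 1.13 for 20% against 10%. Partial dropout of 20% against 10% adds a bias of about 5% in either direction, and the offset reduces it to about 1%. With equal loss the ratio is unbiased or nearly so, but the reported proportions are too low. The shares by arm are assumptions, as are the use of 0.85 as the control rate and Poisson counts. The primary fall-rate analysis and the Fisher's exact outcomes are not affected. This should be corrected before analysis.

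**What to change.** 1. Add `exposure(personyear)` to both `glm` commands, and state that the same applies to the other calendar-based binary outcomes that Table 1 analyses by Poisson regression with robust error variance.
2. Set the binary fall outcomes to missing, not 0, for participants with no calendars. The offset needs this, because log(0) is undefined. They then count toward the 10% trigger and enter the multiple-imputation sensitivity analysis. Report their number by arm.
3. Label the estimate a follow-up-adjusted ratio. With a person-time offset it is not strictly the 12-month risk ratio promised in section 6.

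The cost is two code edits and two sentences in the SAP, with no new data. There are downsides. Participants with no calendars leave the main model, so it is not the full intention-to-treat set. The interval also widens: with SE(log RR) = √[(1 − p1)/(n1·p1) + (1 − p0)/(n0·p0)], the standard error is about 0.19 with all 140 and about 0.21 with 14 PBT and 7 control participants left out. The reported measure departs slightly from a 12-month risk ratio.

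### Participants who return no fall calendar are registered with zero falls, and the SAP text and the Stata code disagree on whether they then count as non-fallers

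*Combined protocol and SAP*

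**What the plan says.** Section 5.1 (Missing data) gives the rule for anyone who sends back no calendar: "For participants who do not return any fall calendars 0 falls and 0 person-years will be registered". For the primary outcome nothing is imputed and "the analysis will be adjusted for follow-up time (days of follow-up will be used as an offset". For the secondary binary outcomes, likewise not imputed, "the modified Poisson regression will be adjusted for person-years (days of follow-up will be used as an offset". The safeguard is conditional: "if more than 10% of data is missing in any outcomes, a sensitivity analysis utilising multiple imputations will be conducted".

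Section 6 opens with "All statistical tests will be performed using an intention-to-treat approach" and says that binary outcomes will be reported as risk ratios.

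The Stata code in section 7 fits the primary model with person-years as exposure: "poisson fallrate ib1.group, irr exposure(personyear". The proportion of fallers is coded as "glm faller ib1.group, fam(poisson) link(log) vce(robust) eform". The version adjusted for age, sex and fall history follows the same pattern. Neither faller model has an exposure or offset term.

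**The concern.** Section 5.1 and the code treat the same people differently. A participant with no calendar has no observed fall outcome, yet the SAP gives that participant an observed-looking value of zero. In a model with a follow-up offset this does no numerical harm, because zero person-years removes the record. In a model without an offset, nothing marks the zero as unobserved.

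The outcome affected is the proportion of fallers, the only secondary fall metric for which section 2.2 states an expectation (50% lower with PBT). The faller code is also the SAP's example for Poisson regression with robust error variance. The fracture and injury proportions in Table 1 use that method and would inherit the problem.

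Two further points follow from the rule. The set behind the primary rate ratio is narrower than the intention-to-treat label suggests. The SAP also does not say whether a registered zero counts as missing for the 10% trigger.

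**Working it through.** **Inputs.** From section 3.1: fall rate 0.85 (taken as the control rate per person-year), 50% reduction, 80% power, 5% significance level (taken as two-sided), 20% dropout, 70 per group. Follow-up is 12 months. The documents give no rate of complete calendar non-return, so every such rate below is an assumption.

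**The plan's own figure.** Rates are 0.85 and 0.425, with sum 1.275 and difference 0.425. Per group, n = (1.960 + 0.842)² × 1.275 / 0.425² = 55.4, rounded up to 56. Then 56 / (1 − 0.20) = 70, which matches. This point does not alter the sample size.

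**Primary model.** A record with y = 0 falls and exposure t = 0 has Poisson mean 0. Its log-likelihood contribution is 0 whatever the coefficients, and ln(0) is undefined as an offset. In a simulated 70/70 data set with 14 PBT and 7 control non-returners:
- dropping them (n = 119) gave an IRR of 0.4705 with SE(log) 0.2483;
- keeping them with exposure 10⁻⁹ gave the same values;
- exposure of exactly 0 could not be fitted.

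The estimate is the same either way, and the people are absent either way.

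**Proportion of fallers, text against code.** Under section 5.1 the offset for a zero-person-year record is undefined, so the record leaves the model. Under the code there is no offset, so a record with faller = 0 stays in. In the same simulated data the coded model on all 140 gave a risk ratio of 0.667 (95% CI 0.44 to 1.02). Among the 119 returners it was 0.750 (0.50 to 1.12).

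**Size in general.** Let p be the proportion of fallers and r the share returning any calendar, assuming non-returners would have fallen as often as returners in their arm. The coded proportion in each arm is p × r, so

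coded RR = (p_PBT / p_control) × (r_PBT / r_control).

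Assuming Poisson falls, p_control = 1 − exp(−0.85) = 0.573 and p_PBT = 1 − exp(−0.425) = 0.346, a true RR of 0.605.

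| Assumed non-return, PBT / control | Factor | Coded RR, no true effect | Coded RR, planning rates |
|---|---|---|---|
| equal, any level | 1 | 1.00 | 0.605 |
| 15% / 5% | 0.85/0.95 = 0.895 | 0.895 | 0.541 |
| 5% / 15% | 0.95/0.85 = 1.118 | 1.118 | 0.676 |
| 14 of 70 / 0 of 70 (extreme) | 56/70 = 0.80 | 0.80 | 0.484 |

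With equal non-return of 14 per arm the ratio holds, but the reported proportions fall from 0.346 and 0.573 to 0.277 and 0.458.

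**The trigger.** Non-return of 15% and 5% in arms of 70 is 10.5 + 3.5 = 14 of 140, exactly 10%. The rule requires more than 10%, so it would not fire on these participants alone, even if they counted as missing. Under a true null (p = 0.573, 70 per arm), the two-sided type I error of the coded model is about 5% with no non-return and 4% at 7/7. For splits that total 14 (PBT/control) it is about 8% at 10/4, 11% at 11/3 and 27% at 14/0.

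**The case against.** The strongest reply is that little of this touches the main result. People without any fall follow-up cannot inform a rate, the primary IRR is the same with or without them, and section 5.1 says openly that missing fall data are not imputed. That stands: for the primary outcome this is a matter of naming the analysis set. A reader might infer that the primary analysis is a complete-case analysis or is biased by the rule. The documents do not support that. Participants with some calendars contribute their observed days through the offset, and only those with none drop out.

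A second reply is that the code lines are labelled as examples, and that nothing says how the faller variable is set for such a record. That also stands. A reader might infer that the planned proportion analysis is certainly biased, or biased towards PBT. It is not certain: following section 5.1 excludes these people, and the direction depends on which arm returns fewer calendars. The conflict between text and code remains, because an analyst can follow only one of them.

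Third, the zero rule sits under the missing-data heading immediately before the trigger, so non-returners are naturally read as missing. That is a fair reading, and the claim that imputation would fail to run is too strong. The wording is ambiguous on this point, and one sentence would settle it.

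Fourth, the non-return rates are assumed. The 20% in section 3.1 is a dropout allowance, not a rate of returning no calendar at all, and complete non-return may be rarer. Section 6 also labels the secondary outcomes exploratory.

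**Conclusion.** The SAP is inconsistent as written. Section 5.1 and the proportion-of-fallers code lead to different analysis sets, and that conclusion needs no assumption about non-return rates beyond there being at least one non-returner coded as a non-faller. The size of any bias does depend on assumptions: the faller variable must be derived from the registered zero, the code must be followed rather than the text, and non-return must differ between arms. At 15% against 5% the risk ratio shifts by a factor of 0.895 or 1.118; at equal non-return it does not shift.

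The primary IRR is numerically unaffected. Its set should be described for what it is, randomised participants with at least one returned calendar. The severity is modest, since the numerical risk falls on secondary proportion outcomes. The correction is worth making because it costs almost nothing and removes a way to reach a wrong estimate by following the plan's own code.

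**What to change.** 1. In section 5.1, replace the zero rule: when no calendar is returned, all fall outcomes are missing, not 0.
2. State that these participants count towards the 10% trigger for the multiple-imputation sensitivity analysis, and report their number by arm.
3. Describe the primary analysis set as all randomised participants with any fall follow-up, in place of an unqualified intention-to-treat label.
4. Make section 5.1 and the code for binary outcomes agree, in both the unadjusted and adjusted models. Simply adding person-years as exposure is not a neutral edit: the estimate then becomes a ratio of fallers per person-year, not the plain risk ratio that section 6 says will be reported. If the offset is kept, the reported measure should be renamed. If the risk ratio is kept, section 5.1 should drop the offset and say how partial follow-up is handled.

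The cost is a few sentences in the SAP and a small code edit. If the trigger is met, the imputation analysis is one the plan already provides for. No new data are needed.

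### Three binary endpoints are assigned only Fisher's exact test, which does not deliver the promised risk ratio and cannot be adjusted; the pre-training laboratory result is handled inconsistently

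*Combined protocol and SAP*

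**What the plan says.** - **Reporting rule (Section 6).** "Binary outcomes will be reported as risk ratios (RR) and 95% CIs". No exception is given.
- **Assigned method (Table 1, secondary fall outcomes).** The Global Impression row has "7-item questionnaire: Fisher’s Exact" for its binary part. "Laboratory-induced slip falls" and the matching trip row are also binary, each with Fisher's exact test and no alternative. The laboratory rows are assessed at the pre-training test, post-training, 26 and 52 weeks; Global Impression at 52 weeks only.
- **Code (Section 7).** The only example for these rows is "tabulate lab_slip_t1 group, exact", where t1 is the pre-training test.
- **Adjusted analysis (Sensitivity analysis, Fall outcomes).** For the primary outcome and "secondary fall outcomes, a sensitivity analysis adjusting for known confounders (age, sex, and previous falls) will be conducted".
- **Other binary fall outcomes (Table 1, Section 7).** Poisson regression with robust error variance, coded with and without age, sex and fall history.
- **Pre-training laboratory result (Table 1 footnote).** One footnote names participant ID as a random effect and limits inclusion to people who did not fall during the pre-training perturbation. In the text as read, its marker appears on no Table 1 row.
- **Context.** Section 3.2 places randomisation after the pre-training tests. Section 6 calls for intention-to-treat analysis throughout and treats secondary results as exploratory.

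**The concern.** A reader of the results would expect a risk ratio and interval for each binary endpoint. For these three rows the plan specifies a method that yields only a p-value. Separate p-values at post-training, 26 and 52 weeks do not show how large an effect is or whether it persists; ratios with intervals would.

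If the authors add a ratio from the two-by-two table afterwards, the test and the interval come from different procedures and can point in different directions near the 5% boundary. The plan does not say which would then be reported as the result.

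For the laboratory outcomes it is also unclear who is analysed. Restricting to pre-training non-fallers, adjusting for the pre-training result and leaving it unused are three different analyses, and the documents do not settle on one.

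**Working it through.** **1. What each method can deliver**

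| Requirement | Fisher, as coded | Robust Poisson, as coded for fallers |
|---|---|---|
| p-value | yes | yes |
| RR with 95% CI | not output; unadjusted RR computable from the counts | yes |
| Adjustment for age, sex, previous falls | not possible | yes, code given |
| Random effect (footnote) | not possible | not in the code given |

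**2. Number per arm used below**

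The documents give no laboratory fall or responder rates and no power for these rows, so the event rates here are assumptions. The number per arm comes from Section 3.1. With rates 0.85 and 0.425 (0.85 read as the control rate), two-sided 5% and 80% power:

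n = (1.960 + 0.842)² × (0.85 + 0.425) / (0.85 − 0.425)² = 55.4, so 56; and 56 / 0.8 = 70.

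This reproduces the stated 70 per group. The G*Power settings are not given, so the route actually used is unknown. The concern does not depend on it; it only supplies 56 assessed per arm.

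**3. Can the test and the interval disagree?**

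Assume 10/56 v 20/56.
- RR = 10/20 = 0.50.
- SE(log RR) = √(1/10 − 1/56 + 1/20 − 1/56) = √0.1143 = 0.338.
- 95% CI = exp(−0.693 ± 1.96 × 0.338) = 0.26 to 0.97.
- Fisher's exact p = 0.054.

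| Assumed table | Fisher p | RR (95% CI) | Robust Poisson p |
|---|---|---|---|
| 10/56 v 20/56 | 0.054 | 0.50 (0.26–0.97) | 0.040 |
| 10/70 v 20/70 | 0.063 | 0.50 (0.25–0.99) | 0.047 |
| 17/56 v 28/56 | 0.053 | 0.61 (0.38–0.98) | 0.040 |
| 6/56 v 12/56 | 0.197 | 0.50 (0.20–1.24) | 0.134 |

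The first three lie near the boundary and show that disagreement is possible, not that it is usual. The source is Fisher's conservatism: with 56 per arm and common event rates of 20%, 30% and 50%, its true rejection rate at nominal 5% is 2.8%, 3.2% and 2.9%.

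**4. Size of the gain if everyone assessed is analysed**

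Exact enumeration at 20% v 40%, 56 per arm: power 57.3% with Fisher and 62.7% with the unadjusted log-RR test, whose size stays below 5%.

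Simulations of 1,500 runs assumed that half of participants fall at pre-training, that later control risk is 60% in those who fell and 20% in those who did not (0.5 × 60% + 0.5 × 20% = 40% overall), and that the true RR is 0.5. Power was about 57% (Fisher), 61–64% (robust Poisson) and 66–67% (with the pre-training fall as covariate). The simulation standard error is about √(0.65 × 0.35 / 1500) = 1.2 percentage points.

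**5. Size if the footnote's restriction applies**

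Under the same assumptions, 56 × 0.5 = 28 per arm remain, with risks of 10% v 20%. Exact power is 8.2% (Fisher) and 6.2% (log-RR test, tables with an arm without events counted as non-rejections).

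**6. The pre-training result, text against text**

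- If the footnote belongs to the slip and trip rows, its random effect cannot be used in Fisher's test. The coded t1 comparison would also be empty, because nobody retained would have fallen at t1.
- If it belongs to another row, such as the overall laboratory fall rate, nothing says how the pre-training result enters the slip and trip analyses.
- On either reading the code applies no restriction. Excluding randomised participants by pre-training result also sits poorly with the intention-to-treat statement.
- The coded example compares groups before randomisation, when any difference is due to chance. Section 2.3 already plans a visual comparison of descriptive data.

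**The case against.** **A risk ratio is still obtainable.** A reader might infer that the plan makes the promised ratio impossible. It does not: the command prints the counts, an unadjusted RR and interval follow from them, and the code is labelled an example. This stands. The gap is an unspecified estimate and a possible clash with the test.

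**The adjusted analysis may not have been promised here.** Section 2.2 lists the secondary fall metrics without laboratory falls or Global Impression, and Section 2.4.2 says that secondary fall outcomes come from the fall calendars. On that definition these rows are outside the adjusted analysis. Against this, Section 2.4.2 also refers to Tables 1 and 2 for the secondary outcomes, and Table 1 puts all three rows under that subheading. The point is arguable, so it holds only conditionally.

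**The pre-training result is not ignored.** A reader might infer from the code that it is used only for the t1 test. The footnote contradicts that, and its missing marker may be a loss in PDF reading, which is not held against the plan. What stands is the inconsistency in step 6. None of this concerns Global Impression, which has no pre-training value.

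**The power gain depends on the analysis set.** Correct: with the restriction, it disappears (8.2% v 6.2%). The same figures show how much information such a restriction could cost.

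**Fisher's test is valid and the endpoints are exploratory.** Both true. This limits the weight of the point but does not remove the mismatch with Section 6.

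**Conclusion.** The concern holds in a limited form. For three binary endpoints the only named method does not produce the risk ratio and interval that Section 6 promises. It also could not be adjusted if the sensitivity analysis is meant to include them. For the two laboratory outcomes, the footnote, the code and the intention-to-treat statement need to be reconciled.

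The size is modest: roughly 4 to 7 percentage points of power from changing the model (57% to 61–64%) and a few more from the covariate (66–67%). These figures rest on assumed event rates, 56 assessed per arm and no restriction to pre-training non-fallers. The main benefit is an effect estimate at each visit that agrees with its test. The documents do not support a stronger conclusion that the trial's findings are at risk: the primary fall-rate analysis and the calendar-based binary outcomes are untouched. The change is worth making but is not critical.

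**What to change.** - **All three rows of Table 1:** replace Fisher's exact test by the Poisson regression with robust error variance already in the SAP. Report RR with 95% CI and the version adjusted for age, sex and previous falls. Say explicitly that the sensitivity analysis covers these rows.
- **Sparse data:** keep Fisher's exact test as a stated fallback for sparse or empty cells.
- **Laboratory slip and trip falls only:** analyse all assessed participants at post-training, 26 and 52 weeks with the pre-training result as a covariate. Replace the footnote's restriction, or reconcile it by stating which row it governs and why. If the restriction were kept, the corresponding pre-training result would be constant and the covariate would add nothing, so one approach must be chosen.
- **Code:** drop the between-group test at t1 and add example lines for the new models.

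The cost is a few lines of SAP text and code, with no new data. The small downside is that the log-link model needs the fallback when events are few.
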